2. PURPOSE OF THE ANALYSES

This statistical analysis plan (SAP) contains detailed information about statistical analysis to be performed to assess whether CNCP patients who receive a MI+CBT-CP intervention have reduced daily morphine equivalent dose (MED), improved physical functioning, and lower pain interference compared to CNCP patients who receive SDM intervention. No formal interim analyses will be conducted. As such, all analyses described will be performed at the end of the study excluding any safety summaries provided for the DSMB which are described in Section 7.4.

3. STUDY OBJECTIVES AND OUTCOMES

3.1. Study Objectives

3.1.1 Primary Objective

1. Test whether CNCP patients who receive guideline-concordant pharmacotherapy with a MI+CBT-CP intervention have greater **opioid dose reduction** relative to their counterparts who receive guideline-concordant pharmacotherapy integrated with SDM.

3.1.2 Secondary Objectives

1. Test whether CNCP patients who receive guideline-concordant pharmacotherapy with an MI+CBT-CP intervention have improved **physical functioning** relative to their counterparts who receive guideline-concordant pharmacotherapy integrated with SDM.
2. Test whether CNCP patients who receive guideline-concordant pharmacotherapy with an MI+CBT-CP intervention have lower **pain interference** relative to their counterparts who receive guideline-concordant pharmacotherapy integrated with SDM.

3.1.3 Additional Objectives Not Specifically Listed in the Protocol Objectives section

1. Comparison of intervention groups for other self-reported outcomes of anxiety, pain intensity, depression, Brief Pain Inventory (BPI) pain intensity subscale and pain interference subscale, intent to taper, and discontinuation of opioid use.
2. While multiple subgroup analyses have an inherent risk of inflating Type I error, this trial offers a unique opportunity to generate hypotheses about the profile of patients most likely to benefit from the intervention. Consequently, planned *secondary* analyses will assess potential differential treatment effects (treatment by subgroup interaction) for two subgroups: 1) defined by participants with comorbid mental health conditions and 2) sex.
3. The study will also include descriptive *exploratory* analyses to explore the heterogeneity within each intervention arm separately on opioid reduction (predictors of response) according to covariates of interest including age, baseline pain score, comorbidities (including physical comorbidities and mental health disorders, and past or current alcohol or other substance abuse and related disorders), those taking other medications, patient health literacy level, BMI, and opioid dose used at baseline in 3 categories consistent with CDC guidelines: low (20-49 MED), moderate (50-89 MED), high (90 or more MED); we will also have a category for very low (1-19 Med); and intervention delivery mode (in-person vs telehealth). Testing for heterogeneity of treatment effects for these subgroups will be considered exploratory as opposed to confirmatory, and the results will be interpreted with appropriate caution
4. Determine if there is a threshold for the number of completed SDM visits or CBT sessions that results in a clinically significant decrease in opioid use from baseline, defined as a decrease of 10 MED daily dose.

3.2 Outcomes

3.2.1 Primary Outcome

The primary outcome is **change from baseline in average daily opioid dose in MED**. The daily MED for each prescription will be calculated by multiplying the quantity of each prescription by the strength of the prescription by the MED conversion factor and dividing it by the total days supply. The primary outcome will be examined at baseline and months **3, 6, 9, 12, 15 and 18** using opioid prescription information recorded in the EHR from 90 days prior to randomization until 18 months after randomization, as provided by the PCORnet common data model (CDM) data warehouse at each site. For each timepoint, the primary outcome will be derived including all opioid medications prescribed 90-days prior to the desired timepoint. The primary timepoint is 12 months; key secondary timepoints at 6 and 18 months.

Derivation of this outcome is provided in section 9.2.

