#### 4.1.4 Other EHR-Derived Outcomes

*Cross-reference: UNC IRBIS Application section A.9.1 (identifiers).*

Other measures collected through the PCORnet CDM include:

- Demographic information (birth date, sex, race, and ethnicity)
- Patient height and weight
- Health care provider information
- Death information (death date and source)
- Health care visit information (visit dates, primary payer, facility type, and provider ID)
- Diagnosis and condition information (condition data and type, diagnosis dates, and associated ICD/CPT codes) for:
  - Mental health disorders, defined by ICD-10 codes (e.g., depression, anxiety, schizophrenia, bipolar disorder, suicide attempt/intent)

- Number and type of CNCP conditions per ICD-10 codes (e.g., back pain, neck pain, headache, arthritis, HIV)
- Alcohol/substance misuse or abuse as measured by ICD-10 codes.
- Overall comorbidity using the Charlson Comorbidity Index per ICD-10 codes
- Opioid prescription information including RxNorm CUI (drug prescribed), prescription dates, dose, units, frequency, route, quantity, refills, and supply days.

We will calculate time to discontinuation of opioids, where discontinuation will be measured based on our previous work, except that the discontinuation will be defined as the first day of a minimum 90-day period with no opioid prescriptions (see Section 5.2 for additional information about the definitions and analyses).

A Schedule of Assessments indicating the timing and source of efficacy, safety, and fidelity measures is presented in **Table 6**.

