#### *Missing Data*

The study will implement multiple procedures to prevent and reduce the amount of missing data and use appropriate statistical procedures to evaluate whether the results are robust to missing data. The risk of missing patient-reported outcome measures has been reduced by limiting the number of visits and assessments to those essential to achieve study goals and using “short” versions of instruments to

reduce burden. It is possible, however, that there may be some nonresponse to the 6- and 12-month patient reported outcome surveys. The sample size calculation assumed as high as 25% non-response at 12 months. EHR-derived data on opioid dosage is expected to be virtually complete based on standard PCORnet data extraction procedures, yet sample size calculations allow for up to 12% missing data at 12 months from lost to follow-up within the EHR or withdrawal of consent for use of EHR data. To reduce the risk of being unable to calculate the primary outcome because of missing or uninterpretable dosing instructions, MED will be derived using only the standardized and highly accurate fields: drug name, strength, and number of pills. In the event of missing medication information for a prescription (such as strength or number of pills), we will impute medication information from the 2 closest prescriptions by date, using an algorithm developed by our clinical content experts, and conduct sensitivity analyses with and without the imputed data.

Logistic regression models will be used to compare the demographic characteristics of participants who provided 18 months of EHR data as compared with participants who were lost to follow-up within the EHR or withdrew consent for study participation to identify possible differential attrition. For primary and secondary outcomes analysis, the planned likelihood-based analysis will produce unbiased results if the data are MAR; that is, not related to the unobserved value of the outcome, but can be related to observed values of the outcome or model covariates.

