5.2 Per-Protocol Population

As in most pragmatic clinical trials, some participants may not adhere to the intervention they were randomized to receive, reducing fidelity to the intervention as designed and potentially changing the effectiveness of the intervention. The most likely form of nonadherence will be absence from group therapy sessions in the MI+CBT-CP arm or with patients in the SDM arm ceasing interaction with the assigned provider. The potential impact of this nonadherence is underestimating the magnitude of the true treatment effect. To assess this, in addition to the ITT analyses, we will also conduct secondary analyses using a per protocol population consisting of participants that met all inclusion/exclusion criteria, and received a substantial portion of the randomized intervention, defined as at least 4 completed SDM visits and at least 4 completed MI or CBT sessions (out of a total of 1 MI and 8 CBT). Note that the inclusion criterion for baseline MED is based on the most recent prescription, while the baseline value for MED in the analysis is the average MED for the past 90 days. Having a baseline value < 20 is not a protocol violation when the sites indicated that inclusion criterion was met based on the most recent prescription when the patient was assessed. A sensitivity analysis on the per-protocol population will also be conducted by defining this population as those who met all inclusion/exclusion criteria and completed at least 3 SDM visits and at least 3 MI or CBT sessions. This sensitivity analyses are included as many SDM participants may only complete 3 visits with their provider throughout the 12-month intervention phase in the event their opioid prescriptions can be renewed over a 3-month period without an actual clinic visit.

The per-protocol analysis provides a better estimate of the true efficacy of an intervention (i.e., among those who completed the treatment as planned) (Ranganathan, Pramesh, & Aggarwal, 2016). No other analysis populations are defined for this protocol.

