9.2 Variable Definitions

The table below provides a description of the study endpoints and subgroup categories, including data type and derivation. More information regarding these variables is provided in the analysis dataset specification file.

Variable	Type	Definition
Primary Outcome		
Change in opioid dose (based on average daily MED) from baseline to 12 months post-randomization	Continuous	
The primary outcome will be derived from EHR data from the Mid-South CDRN data warehouse. Total morphine equivalents for each prescription will be calculated by multiplying the quantity of each prescription by the strength of the prescription (milligrams of opioid per unit dispensed). The quantity-strength product is then multiplied by conversion factors to estimate the milligrams of morphine equivalent to the opioids dispensed in the prescription. The total average dose in morphine equivalents per day supplied is calculated by summing the morphine equivalents for each prescription filled during a given period and dividing by the number of days supplied. The below algorithms further describe derivation of the primary outcome measure:
 $\text{One Prescription's MED Daily (MEDD)} = \frac{(\text{Strength per unit}) \times (\text{Quantity dispensed}) \times (\text{MME Conversion factor})}{(\text{Days Supply})}$ $\text{Avg. MEDD per Timeframe} = \frac{(\text{Multiply each RX's MEDD by Days Supply}) \text{ then } (\text{Sum all RX's Total MEDD for those prescriptions within timeframe})}{\text{Total number of days in timeframe}}$ 
Opioid dose will be calculated as the prescribed milligrams of daily MED averaged over the 90 days prior to randomization and averaged over 90-days for the time periods of 3, 6-, 9-, 12-, 15- and 18-months post randomization.
 
We expect no missing prescriptions, yet some participants might not have complete data because (a) they discontinued and removed consent to use data after that date, (b) they were lost to follow-up and may have moved out of the clinic's care, (c) the last CDM transfer did not contain their data up to 18 months past baseline or (d) they discontinued taking opioids. Cases of (d) will be identified by the response to the T2 and T3 survey item G20 "Are you currently taking an opioid medicine now?". If the response indicates "no" and opioid prescriptions last dose date ends before month 18, then an MED of zero will be assumed for all days after the last dose date to Month 18 (or date participant removed informed consent, if applicable). Otherwise, if there is not a "no" response

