Substance Use Disorders Flag(s)	Binary	
Includes an indicator for any substance use disorder recorded as a diagnosis in the EHR, as well as binary indicators for the presence in the EHR of each of the following: alcohol use disorder and substance use disorder.
 
The ICD-10 codes used to identify Substance Use Disorders was pulled from the Healthcare Cost and Utilization Project Agency for Healthcare Research and Quality (H-CUP-AHRQ) website (https://hcup-us.ahrq.gov/toolssoftware/ccs10/ccs10.jsp#download)

Age	Continuous and categories	
As reported on the T1 (baseline) survey and captured in REDCap.
 
Age category will also be calculated as:
 
 < 50 50-64 >= 65
Intervention Delivery Mode	Categorical and Binary	
Due to the COVID-19 pandemic, the study began offering telehealth intervention visits beginning in early-May 2020. The intervention visit Case Report Forms (CRFs) were modified to document if a specific intervention visit was administered via telehealth or in-person visit. Since the CRFs were not modified until early-August 2020, all visits up-to-that point will be defined as in-person visits. Descriptive statistics of intervention delivery mode by intervention will be displayed (in-person only, telehealth only, and mixed mode); however, for adjusted analyses, mixed mode will be combined with telehealth to create a binary classification variable.

Variable	Type	Definition
Baseline Opioid MED categories	Ordinal	See the first row in this table regarding the derivation of average daily opioid prescription (in MED). Prescriptions provided 3-months, or 90-days prior to randomization will be considered a participant's baseline opioid MED, classified as None (0 MED), Very low (1-<20 MED) Low (20 - <50 MED), Moderate (50 - <90 MED), and High (90+ MED).
BMI	Continuous and categories	
Derived based on the participant's weight and height obtained from the EHR data (pulled within 90-days of the randomization date).
 
BMI category will also be calculated as:
 
 underweight: <18.5 normal 18.5 - < 25 Overweight 25 - < 30 Obese 30 - <40 Extremely obese >=40 
A dichotomous flag will also be calculated for BMI obese vs not obese.

Sex	Binary	As collected from the T1 (baseline survey); based on birth certificate.

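### SAP 9.2 defines the primary dose measure with two conflicting denominators and no rule for supply that crosses a window edge; under the displayed algorithm, refill timing alone can move a stable patient's score by more than the 10 MED target.

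*SAP*

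**What the plan says.** SAP 3.2.1 decides which prescriptions belong to a window: "For each timepoint, the primary outcome will be derived including all opioid medications prescribed 90-days prior to the desired timepoint". The baseline dose row of SAP 9.2 follows the same order-date logic: "Prescriptions provided 3-months, or 90-days prior to randomization will be considered a participant's baseline opioid MED".

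The primary-outcome cell of SAP 9.2 then gives the derivation twice. In the prose, the average daily dose is "calculated by summing the morphine equivalents for each prescription filled during a given period and dividing by the number of days supplied"; protocol 4.1.1 has the same rule. The algorithm displayed beneath multiplies each prescription's daily dose back by its days supply, instructs the analyst to "Sum all RX's Total MEDD for those prescriptions within timeframe", and divides by "Total number of days in timeframe".

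Neither version says what to do with supply that runs across a window edge. SAP 9.2 has day-level wording only for days after the last dose date: zero MED if the participant reports on the T2 or T3 survey that opioids have stopped, missing otherwise. Refills are among the extracted fields ("prescription dates, dose, units, frequency, route, quantity, refills, and supply days", protocol 4.1.4) but enter neither version. Protocol 5.3.3, Missing Data, adds that "MED will be derived using only the standardized and highly accurate fields: drug name, strength, and number of pills", a list without days supply.

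**The concern.** In the displayed algorithm days supply cancels. Each order contributes strength × quantity × conversion factor, all of it to the window of its order date, over a fixed denominator. A 30-day script ordered the day before randomisation counts wholly as baseline, although nearly all of it covers post-randomisation days. One ordered five days before a window opens adds nothing to that window, although 25 of its days fall inside.

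This quantity supplies both ends of the single primary test. It also feeds the comparison in SAP 9.4 of the share of participants with a 10 MED decrease, and the baseline dose categories. If the prose rule was intended instead, the measure behaves quite differently, and the SAP does not say which governs.

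**Working it through.** **Inputs.** Mean baseline dose 55 mg/day (protocol 5.4). Target difference 10 MED, adjusted SD 40, 253 per arm, 80% power (SAP 6). Two-sided 5% test (SAP 7.6). Supply generally 30 days (protocol 5.2.3). Window 90 days (SAP 3.2.1). The variation in order intervals is not in the documents and is assumed.

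**1. The plan's sample size.** n per arm = 2 × (1.960 + 0.842)² × 40² / 10² = 252 by the normal formula; the noncentral t gives 253. Then 506 × 1.2 = 607.2, so 608. These figures reproduce and are not in dispute.

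**2. Displayed algorithm, stable patient.** With k orders of S days at dose D, score = k × S × D / 90. For S = 30 and D = 55, each order is worth 30 × 55 / 90 = 18.3 MED:

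| Orders in window | Score (MED) |
|---|---|
| 2 | 36.7 |
| 3 | 55.0 |
| 4 | 73.3 |

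One order crossing one edge therefore moves the score by 18.3 MED. An exact 30-day cycle always puts three orders in a 90-day window and gives no error.

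**3. Prose rule, same patient.** Score = (k × 30 × 55) / (k × 30) = 55 whenever k is at least 1. Refill timing has no effect. With k = 0 the score is 0/0.

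**4. Simulated size under the displayed algorithm.** Constant 55 MED, 30-day scripts, random phase, windows day -90 to 0 and day 275 to 365:

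| Assumed SD of order interval | SD of spurious 12-month change | Shift of 10 MED or more, either way |
|---|---|---|
| 1 day | 5.6 | 9% |
| 3 days | 9.6 | 24% |

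The mean spurious change is about 0. At an SD of 3 days, about 12% are scored as a decrease of 10 MED or more although nothing changed.

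**5. Power at 253 per arm.** Power = Φ(10 / (SD × √(2/253)) − 1.96).
- SD 40: Φ(2.81 − 1.96) = 80.3%.
- Adding the timing variance of the 12-month window (SD 6.8 at an interval SD of 3 days): √(1600 + 46) = 40.6, giving 79.2%.
- Adding the whole change variance as an upper bound: √(1600 + 92) = 41.1, giving 78%.

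The planned 40 may already contain some of this noise.

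**6. Baseline under a day-level rule.** SAP 3.2.1 takes prescription data from 90 days before randomisation. For 30-day scripts in random phase, supply ordered earlier covers on average the first 15 days of the window. Without it the baseline loses 15 × 55 / 90 = 9.2 MED and reads about 46 rather than 55. Later windows have no such loss.

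**7. Refills.** Under the displayed algorithm, 30 MED/day ordered as 30 days plus two refills scores 30 × 30 / 90 = 10. The documents do not say how often orders carry refills.

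**The case against.** The strongest reply is that the displayed algorithm is only one of the plan's statements. The prose in the same cell and protocol 4.1.1 remove the timing effect in any window that has an order. The last-dose-date wording, and the description in SAP 9.3 of month 12 as the average over months 9 to 12, suggest day-level thinking. Further detail sits in a dataset specification file that is not part of these documents. This stands as far as it goes: the SAP cannot be said to have adopted the order-date artefact outright. But the prose is not a safe fallback, because it leaves empty windows undefined, and the last-dose-date wording does not cover ordinary window edges.

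Three stronger readings are tempting and are not supported.

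- **Many participants hold 90-day supplies and so score zero or double.** A reader might infer this from SAP 5.2, which expects fewer visits "in the event their opioid prescriptions can be renewed over a 3-month period without an actual clinic visit". That passage concerns renewal without a visit, and monthly renewals fit it equally well. The supply length the protocol states is generally 30 days. Larger losses for longer supplies depend on assumption.
- **The arm comparison is biased.** Mean spurious change is about zero and arms are randomised within site. Protocol 6.2.1 allows more visits for tapering SDM patients, so different ordering patterns are conceivable, but nothing shows them.
- **The zero and very-low baseline categories prove the artefact.** They are compatible with it, but SAP 5.2 gives another reason for baselines under 20: eligibility uses the latest prescription, while baseline is a 90-day average.

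**Conclusion.** The point holds as a conflict of definition with a missing edge rule. SAP 9.2 has two denominators that can give different values for the same patient, and neither is adequate alone. If the displayed algorithm is programmed with SAP 3.2.1, one order crossing an edge is worth 18.3 MED for a 55 MED patient on 30-day scripts.

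The consequence is mainly noise. The cost to the primary test is small, about one percentage point of power and about two at the upper bound. The 10 MED responder comparison is hurt more, since 9% to 24% of stable patients would shift by that amount in one direction or the other. These percentages rest on assumed interval SDs of 1 to 3 days and vanish with perfectly regular 30-day cycles. It still warrants correction before analysis, because it determines both values in the primary outcome and leaves the programmer to choose.

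**What to change.** In SAP 3.2.1 and 9.2, replace both rules with one day-level rule:

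- Spread each prescription's daily MED over its days supply from its start date.
- Start an early renewal of the same drug when the previous supply runs out, so that overlap days are not counted twice.
- Add concurrent prescriptions of different opioids.
- Average over the days of the window, including supply carried in from earlier orders.
- Keep the existing handling of days after the last dose date.
- Apply the same rule at baseline, with the extraction reaching back before day -90.
- State how authorised refills count, and run a sensitivity analysis with and without them.

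The early-renewal rule is needed. In a scenario of 90-day supplies with an assumed interval SD of 10 days, simply summing active scripts raises the share of stable patients shifting by 10 MED or more from 16% to 23%; starting renewals at run-out cuts it to about 3%.

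The cost is SAP wording, derivation programming and a slightly longer baseline extraction. The 12-month prescription query in protocol 3.1 feeds a local pre-enrolment database, so it may not supply the look-back. The rule also leans more on supply days, which protocol 5.3.3 leaves off its list of accurate fields and SAP 7.3 allows to be derived by assumption. A continuously supplied stable patient would then score 55 in every window.

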3.2.2 Secondary Outcomes

1. Change in self-reported physical functioning, as collected via the **PROMIS-PF 8-item Short Form**, from pre-intervention (baseline) to post-intervention (months 6 and 12). The primary timepoint is 12 months.

2. Change in self-reported pain interference, as collected via the **PROMIS-PI 8-item Short Form**, from pre-intervention (baseline) to post-intervention (months 6 and 12). The primary timepoint is 12 months.

